## 6. Study Primary Endpoints

The primary objective is to assess the impact of Apollo / Artemis MIES upon clinical outcomes in patients with supratentorial intracranial hemorrhage with primary endpoints defined as:

- Rate of recruitment over a two-year time span following first patient enrollment
- Rate of successful 180 day follow up obtainment.

- Statistical details can be found in section 7.2.

## **6.1**            *Analysis of Primary Endpoint*

### **6.1.1**        **Definition of Analysis Samples**

#### 1. Target Population

The target population for the Apollo / Artemis MIES trial are patients 22-84 years of age who have a diagnosis of spontaneous, non-traumatic, intracerebral hemorrhage (ICH) ranging in volume between 30 and 80 cc, with an associated significant neurological deficit (NIHSS  $\geq 6$ ) who do not require emergent open surgical decompression related to uncontrolled intracranial pressure or mass effect.

## **7. General Statistical Considerations**

### **General Design**

The Apollo / Artemis MIES Trial is a multicenter, single arm feasibility study investigating the potential efficacy of Apollo / Artemis MIES to improve clinical outcomes in patients with spontaneous, non-traumatic, ICH presenting within 24 hours. The primary hypothesis to be tested is that Apollo / Artemis MIS patients can be recruited and followed successfully for 180 days.

### **7.1**            *Sample Size Estimation for the Primary Outcome*

#### **Sample Size Calculation**

The Apollo / Artemis MIES Trial is a prospective, multi-center, single-arm feasibility trial investigating enrollment of the Apollo / Artemis MIES in patients with spontaneous, non-traumatic, ICH presenting within 24 hours. Up to 50 subjects will be enrolled in this study. The primary outcome assessed at trial completion will be successful capture of 180 day modified Rankin score (mRS) for those 50 patients enrolled in the study. Additionally, we will analyze the proportion of patients achieving mRS of 0-3 and 90 day mortality.

### **7.2**            *Statistical Evaluation*

#### **Statistical Analysis of Primary Outcome**

Two-sided 95% confidence intervals will be calculated for the proportion of subjects with captured mRS scores at the 180-day follow-up visit using the exact binomial distribution.

#### **Statistical Analysis of Secondary Outcomes**

Secondary efficacy analyses will include 180-day global disability assessed via mRS, analyzed as the proportion of patients achieving mRS of 0-3. Two-sided 95% confidence intervals will be calculated for the proportion of subjects with mRS scores of 0-3 at the 180-day follow-up visit using the exact binomial distribution. The Kaplan-Meier Curve will be generated to assess the 90 day mortality. With the date of enrollment set at day 0, and any death occurring on or before day 90 will be included as a death.

## **Subsequent Statistical Analysis**

Statistical analysis of the SIS-ADL, SIS-mobility, EQ-5D-5L, and Length of Stay will be analyzed with confidence intervals.

Other pre-specified analyses will be performed as outlined in the statistical plan.

### **7.3 *Missing Data and Imputation Methods***

Every effort will be made to keep all missing data, particularly the Day 180 outcomes, to a minimum. Despite the clinical sites' best efforts, some missing data may be inevitable mainly due to lost-to-follow-up (LTFU). The number and proportion of subjects eligible for and compliant with each follow-up examination will be presented. Subjects who withdraw from the study will be tabulated with reasons for withdrawal. Additional details will be provided in the Statistical Analysis Plan (SAP).

### **7.4 *Secondary Statistical Analysis***

Statistical analysis of the raw Rankin outcome scores of 0 to 6 (with 5 and 6 collapsed) will be conducted with an adjusted ordinal logistic regression model (proportional odds model). This analysis will be adjusted using key baseline variables. The odds ratio and corresponding 95% confidence interval will be presented for the treatment effect.

Group differences will be analyzed by the non-parametric Wilcoxon rank sum test for the following:

- SIS-ADL
- SIS-mobility
- EQ-5D-5L
- Length of Stay

Other pre-specified analyses will be performed as outlined in the statistical plan.

### **7.5 *Safety Analysis***

#### **7.5.1 *Safety Outcomes***

##### **Safety outcomes**

Several specific adverse events are monitored throughout the study. However the primary safety outcome to be assessed at completion of the trial will be death within 90 days.

#### **7.5.2 *Interim Safety Monitoring***

##### **7.5.2.1 *Stopping the Trial Based on Interim Safety Data***

The Trial Operating Committee (TOC) and Data Safety Monitoring Board (DSMB) will receive periodic safety reports of all AEs and SAEs. In addition, the following specific endpoints will be assessed by the medical monitor and presented:

- Death (all cause) within 90 days of enrollment
- Death within 7 days of enrollment: Immediate periprocedural death

- Symptomatic Re-Hemorrhage or New Hemorrhagic Event: any new intracranial hemorrhage or increase in size of pre-existing hemorrhage (IPH, IVH or extra-axial bleed) within 90 days associated with an increase of 4 or more points on the NIHSS or GCS increase  $\geq 2$  persisting for at least 24 hours and/or requiring emergency surgical decompression or resulting in death.
- Symptomatic Evolution of Perihematomal Edema: Edema with increased mass effect or uncontrolled ICPs within 90 days requiring emergency surgical decompression NOT related to new or increased hemorrhage (i.e. edema related) associated with an increase of 4 or more points on the NIHSS or GCS increase  $\geq 2$  persisting for at least 24 hours and/or requiring emergency surgical decompression or resulting in death.
- Symptomatic Ischemic Stroke: A new ischemic stroke (ipsilateral, contralateral; contiguous with bleed/operative site or remote; cortical, subcortical or perforator distribution) within 9s associated with an increase of 4 or more points on the NIHSS or GCS increase  $\geq 2$  persisting for at least 24 hours and/or requiring emergency surgical decompression or resulting in death.
- Surgical complications related to Apollo / Artemis MIES: Surgical site infection, brain abscess or confirmed meningitis, or documented complication(s) deemed specifically related to the procedural anesthetic (medication, access or intubation related) within 90 days.

Additional details of the monitoring plan will be included in the study MOP. Additional details regarding the DSMB structure and stopping rules will be included in the DSMB charter.

## 7.6 *Blinding*

This study is not blinded. Blinding is difficult, if not impossible, from a clinical perspective. It is not possible to blind the Investigator who treats the patient, the clinical staff or the research team. Additionally, physicians treating subjects who experience an adverse event after must know how the hemorrhage was treated in order to effectively report the adverse event and plan further treatment. Blinding the study is not required for interpretation of study outcomes.

## 8. Study Withdrawal

Subjects may be terminated or withdrawn from the study for the following reasons:

- Voluntary withdrawal of consent— meaning that a subject voluntarily chooses not to participate further in the study. All data collected up to the withdrawal of consent will be maintained in the study database.
- Lost to follow-up — defined as a subject who is more than one month late to a study visit and for whom 5 documented telephone attempts to contact the subject and at least one certified letter were unsuccessful.
- Subjects may also be withdrawn at the investigator’s discretion if within their best interest.

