### **3. Objectives**

#### **3.1 Primary Objective**

- The primary objective is to provide an initial assessment of enrollment and follow up feasibility for the patient population being treated with the Apollo / Artemis MIES. Primary Endpoint: rate of successful obtainment of modified Rankin score (mRS) at 180 days

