#### **4.4 Study Visits**

Subjects enrolled to this study will follow the below visits schedule according to their institutional standard of care for stroke patient follow-up.

- Pre-Treatment
- Procedure
- Post procedure (within 24 hours, Apollo / Artemis MIES patients)
- 7 days post-enrollment or Discharge (whichever comes first)
- Discharge (if beyond 7 days)
- 3 month follow-up (+/- 14 days)
- 6 month follow-up (+/- 21 days)
- 12 month follow-up (+/- 35 days)
- 

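### Section 8 allows a patient lost at the 3-month visit to be terminated before the 180-day mRS, a primary endpoint, falls due

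*Combined protocol and SAP*

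**What the plan says.** Section 3.1 names the "Primary Endpoint: rate of successful obtainment of modified Rankin score (mRS) at 180 days". The synopsis and Section 6 list two primary endpoints: "Rate of recruitment over a two-year time span following first patient enrollment" and "Rate of successful 180 day follow up obtainment". Section 7.1 sets the outcome as "successful capture of 180 day modified Rankin score (mRS) for those 50 patients enrolled in the study". Section 7.2 gives an exact two-sided 95% binomial interval for the "proportion of subjects with captured mRS scores at the 180-day follow-up visit", and gives no analysis for the recruitment rate.

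The visit list in Section 4.4 has "6 month follow-up (+/- 21 days"), and the 3-month visit has 14 days either side. Table 1 repeats both windows.

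Section 8 opens with "Subjects may be terminated or withdrawn from the study for the following reasons". Loss to follow-up is one of those reasons, "defined as a subject who is more than one month late to a study visit", with two further conditions that must also be met: five documented calls and at least one certified letter, all unsuccessful.

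Section 8.1 asks sites to contact anyone who misses a visit and find out why. Section 7.3 commits in general terms to keeping missing data low, above all at day 180, and leaves further detail to a statistical analysis plan.

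**The concern.** The study exists to learn whether these patients can be recruited and followed to 180 days. The loss rule is not tied to the 180-day visit; it can be met at any visit. A patient who cannot be reached around month 4 may be reachable in month 6, for example after a transfer between rehabilitation, nursing care and home, or through a representative. If the site has already closed the patient out, that chance is not taken and the patient counts as not captured.

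Termination is optional, so centers may also differ. One may close a patient out at month 4 while another keeps trying. With up to 10 centers and 50 patients, the capture rate would then depend partly on local use of the withdrawal rule as well as on how easy the patients are to follow.

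**Working it through.** **Inputs.** Visit windows come from Section 4.4 and Table 1. The loss rule comes from Section 8. The denominator of 50 comes from Section 7.1 and the interval method from Section 7.2. Two assumptions are needed: a month is 28 to 31 days, and lateness runs either from the target day or from the end of the window, because Section 8 does not say which. The plan gives no target capture rate, precision or loss rate behind the 50, so it has no figure to reproduce.

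**Step 1: visit windows.**
- 3 months: 90 ± 14 = days 76–104.
- 6 months: 180 ± 21 = days 159–201.

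**Step 2: earliest point at which loss at the 3-month visit can be declared.**
- From the target day: 90 + 28 = 118 to 90 + 31 = 121.
- From the window end: 104 + 28 = 132 to 104 + 31 = 135.

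These are earliest dates, because the calls and the letter must also have failed.

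**Step 3: distance to the primary assessment.**
- To the opening of the 6-month window: 159 − 135 = 24 days at the least, 159 − 118 = 41 days at the most.
- To day 180: 180 − 135 = 45 days to 180 − 118 = 62 days.

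Calendar months do not change the answer. With a 3-month target as late as day 92, the latest threshold is 92 + 14 + 31 = day 137, still before day 159.

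**Step 4: effect on the primary estimate.** One patient is 1/50 = 2 percentage points. The exact limits for x captured of n are the 2.5% quantile of Beta(x, n − x + 1) and the 97.5% quantile of Beta(x + 1, n − x). The counts below are assumed, for scale only:

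| Captured of 50 | Rate | Exact 95% CI |
|---|---|---|
| 45 | 90% | 78.2–96.7 |
| 42 (three fewer) | 84% | 70.9–92.8 |
| 40 (five fewer) | 80% | 66.3–90.0 |

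**Step 5: the same rule at the 6-month visit.** The window closes on day 201. Loss can be declared after 180 + 28 = 208 to 180 + 31 = 211, or after 201 + 28 = 229 to 201 + 31 = 232. An mRS taken from day 202 up to those dates is outside the visit window while the patient is not yet lost. Section 7.2 does not say how to classify it.

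**The case against.** The strongest defence is that the loss definition is demanding. Lateness alone does not suffice: six documented contact attempts must have failed, and even then termination is only permitted. Many patients who meet all of this would not be found at 180 days either. Section 8.1 requires contact after a missed visit, and Section 7.3 singles out day-180 data for special effort. All of this stands, and it limits the number of patients at risk. It does not close the gap: Section 8.1 concerns the reason for the missed visit, Section 7.3 states an intention, and neither requires a new attempt at 180 days once a patient has been closed out.

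A reader might also infer that the 21-day window and the one-month rule contradict each other. They do not at 6 months: one sets when a visit is on time, the other gives a ground for withdrawal, and a site can follow both. Section 7.2 ties capture to the 180-day visit, so the natural reading is that the visit window governs. Section 7.1 supplies the all-enrolled denominator and Section 5.9.1 gives death an mRS of 6. What remains on capture is missing detail: assessments after day 201 are unclassified, and Section 7.2 does not say outright that a death counts as captured. The separate statistical analysis plan that Section 7.3 mentions may address this.

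**Conclusion.** The point holds in a limited form. Under every reading of one month and either starting point for lateness, Section 8 permits termination after a missed 3-month visit 24 to 41 days before the 6-month window opens. This can lower the 180-day capture rate by 2 points per patient affected, at 50 enrolled.

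How many patients that would be cannot be computed, because the documents state no expected loss rate. The counts in the table are assumed, and no target rate or decision threshold is stated for them to cross. It would go too far to infer that the capture rate mainly reflects the withdrawal rule; it depends on the rule only in part. It would also be wrong to treat mRS capture as the sole primary endpoint, since the synopsis and Section 6 add the recruitment rate. The change is worth making because it is cheap and protects the quantity the study is meant to measure. The definition of capture is a clarification.

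**What to change.** **Section 8.** State that being lost at an earlier visit does not end participation for the 180-day assessment. Contact attempts, including to the legally authorized representative and for vital status, are made again within the 6-month window unless consent has been withdrawn. State also whether lateness runs from the target day or from the end of the window.

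**Section 7.2, as a clarification.** Define capture as an mRS obtained on days 159–201, or a documented death by then (mRS 6), over all enrolled patients. Report assessments after day 201 separately as a late-capture rate.

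**Cost.** A few sentences of wording and a few further telephone attempts for each patient affected. No extra patients or visits are needed. Holding late assessments out of the numerator may make the reported rate slightly less favourable.

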### 8.1 *Unattended Visits*

Any study subject who does not attend a scheduled follow-up visit should be contacted by site personnel to determine the reason for the missed appointment(s). If the missed visit was due to a serious adverse event, (e.g., re-hospitalization) an AE Case Report Form (CRF) must be completed and any reporting requirements met.

## 9. Data Safety Monitoring Board (DSMB)

A DSMB will be comprised of 4 members not participating in the trial and will include neurovascular specialist physicians and a statistician. The DSMB will exercise review of the overall safety of the trial, periodically review all adverse events occurring in the trial, and make recommendations to adjustments in the study protocol, should any be

considered necessary for safety or other related reasons. Additional details will be specified in the DSMB charter.

### **10. Trial Operating Committee (TOC)**

The TOC will consist of the study PIs, statistical PI, project managers, data managers, and others deemed necessary in overseeing the day-to-day operations of the trial. The TOC will review study progress, study conduct at individual clinical sites, other clinical site performance measures, and blinded DSMB reports.

### **11. Steering Committee (SC)**

The SC will be comprised of the trial PI's and selected principal investigators from participating centers. The SC will be responsible for overall supervision and execution of the trial including adherence to protocol, progress of enrollment, patient safety and consideration of new information. Daily trial management is the responsibility of the TOC. It will provide key input to the SC for study planning, execution and data presentation.

### **12. Study Management**

As the study Principal Investigators, [name] MD, [name] MD PhD, and [name] MD, have overall responsibility for the conduct of the study according to 21 CFR 812, 21 CFR Part 50, Good Clinical Practice (GCP) Guidelines (Guidance for Industry, E6 Good Clinical Practice Consolidated Guidance, ICH, April 1996), ISO 14155: Part 1 and 2, the Declaration of Helsinki, Medical Device Directive, Annex X, FDA and all applicable regulatory requirements. For this study, the PIs will have certain direct responsibilities and will delegate other duties to appropriately qualified individuals. All personnel participating in the conduct of this clinical trial will be qualified by training, education, and experience to perform his or her respective tasks.

\*NOTE: A complete list of participating investigators will be maintained and will be available upon request.

### **13. Investigator Responsibilities**

The Investigator(s) shall be responsible for the day-to-day conduct of the investigation as well as for ensuring that the investigation is conducted according to all signed agreements, applicable elements of ISO 14155, the Clinical Investigational Plan, applicable FDA regulations, and the principles that have their origin in the Declaration of Helsinki.

The investigator is also responsible for having control of the device under investigation, for protecting the rights, safety and welfare of subject's under the investigator's care and for obtaining informed consent in accordance with 21 CFR Part 50. Each Investigator must sign the Investigator Agreement (or an equivalent and a Financial Disclosure) prior to becoming eligible to enroll subjects in this trial.

Responsibilities of the Investigator include, but are not limited to:

Ensuring that IRB approval is obtained prior to undertaking the trial at a clinical site; and, that participation of a subject in a clinical trial includes obtaining written informed consent prior to enrollment, and/or other non-standard of care study-related assessments;

Providing the TOC with accurate and complete financial information per 21 CFR Part 54; Ensuring that all personnel assisting with the clinical trial are adequately informed and understand their trial-related duties and functions;

It is recommended that each site identify a study coordinator for this study. Working with and under the authority of the clinical site Principal Investigator, the study coordinator assures that all study requirements are fulfilled, and is the contact person at the site for all aspects of study administration.

The Investigator will allow direct access to source data/documents for trial related monitoring, audit, IRB/EC review and regulatory inspection. Also, the investigator will allow auditing of their clinical investigational procedure(s).

#### **14. Required Documents from the Investigator**

At a minimum, the investigational site will provide the following documents to the TOC:

- 1) Signed Investigator Agreement
- 2) Written and dated IRB/EC approval,
- 3) Written and dated IRB/EC approval for ICF document
- 4) IRB/EC approval for any other written documents to be provided to the study subject (e.g., advertising),
- 5) HIPAA documentation,
- 6) \*Investigator and Co-Investigators' current Curriculum Vitae,
- 7) Current medical licenses,
- 8) Any other relevant documents requested by the TOC or the reviewing IRB/EC or other regulatory authorities,
- 9) FDA Form 3454 or 3455 (or equivalent) regarding financial interests
- 10) Fully executed contract.
- 11) Ongoing IRB approval documents
- 12) Source Documents for data verification
- 13) Site Delegation of Authority Log

A site may not begin study participation until all of the above listed documents have been provided to the study management team.

\* With regard to the Sub-Investigators current CVs, the study may begin once the CV of the site PI, IRB approval and IRB approved consent and privacy statement, the investigator's agreement, Medical License, and financial disclosures, fully-executed contract, and others listed above, have been received. No additional Investigators may participate in the study, however, until a copy of their CV and all other required documents have been provided to the TOC.

#### **15. Investigator Records**

The Investigator must ensure that all study subject records are stored for at least 6 years after the end of the clinical study. To avoid error, the study site should contact [name] MD prior to the destruction of study records to ensure that they no longer need to be retained. In addition, [name] MD should be contacted if the Investigator plans to leave the investigational site so that arrangements can be made for the handling or transfer of study records.

The Investigator will also maintain original source documents from which study-related data are derived, which include, but are not limited to:

- Clinic progress notes recording subject's medical history and medications;
- Medical charts with operative reports and condition of subject upon discharge;
- Medical records regarding AEs/SAEs, including treatment and clinical outcome;
- Results of diagnostic examinations, imaging (such as x-rays, MRIs), as well as the report of the radiologist's reading/interpretation of diagnostic imaging;
- Signed notes of phone calls and/or correspondence indicating investigational site's attempts to follow study subjects at the required follow-up visits until subject's participation in the study is complete or terminated;
- Records relating to patient death (e.g., death certificate, autopsy report, if available, or terminal medical records).

## **15.1 Data Collection**

### **15.1.1 Data Management Overview**

Data management will be handled by the MSMC Stroke Clinical Research Group, which is housed in the Department of Neurological Surgery at the Mt. Sinai Medical Center (MSMC), and its representatives. All activities will be conducted in coordination with the study PI, the sites, and the TOC. The data validation procedure will be implemented in two stages. First, the automated data checks will flag items that fail a rule, and the rule violation message will appear on the data entry screen at the time of data entry. The Study Coordinator at a site will see these rule violations and will be required to provide a response. His/her choices are to: (1) correct the entry immediately; (2) correct the entry at a later time; or (3) if the entered data are confirmed to be correct, dismiss the rule by checking that option provided by the Research Electronic Data Capture, REDCap system. Any changes made to the data will have a full audit trail. Second, for some checks that are more complicated, additional consistency checks will be run periodically after data entry occurs at the site. All data items that fail the programmed consistency checks will be queried via the data clarification request (DCR) process initiated by the MSMC data managers and/or their representatives. Site Monitors will also be able to generate DCRs when discrepancies are found during source document verification. The DCRs will be generated, communicated to the sites, and resolved within the secure study database.

In addition to the study database, MSMC will provide the site staff password protected access to a standard set of web-enabled tools, including subject visit calendar, subject accrual status, case report form completion status, and outstanding DCR status pertaining to their respective sites.

